## **8.6 Pharmacokinetics**

PK parameters will not be evaluated in this study.

## **8.7 Pharmacodynamics**

Pharmacodynamic parameters will not be evaluated in this study.

## **8.8 Future Biomedical Research Sample Collection**

If the participant provides documented informed consent for FBR, the following specimens will be obtained as part of FBR:

- DNA for future research

## **8.9 Planned Genetic Analysis Sample Collection**

Not applicable.

## **8.10 Biomarkers**

Biomarkers are not evaluated in this study.

## **8.11 Health Economics Medical Resource Utilization and Health Economics**

All-cause hospitalizations and emergency room visits must be reported in the electronic case report form (eCRF), from the time of treatment allocation through 90 days following cessation of study intervention, or 30 days following cessation of study intervention, if the participant initiates new anticancer therapy, whichever is earlier.

## **8.12 Visit Requirements**

Visit requirements are outlined in Section 1.3 (SoA). Specific procedure-related details are provided in Section 8.

### **8.12.1 Screening**

Documented consent/assent must be obtained prior to performing any protocol-specific procedure. Results of a test performed prior to the participant signing consent/assent as part of routine clinical management are acceptable in lieu of a screening test if performed within the specified time frame. Screening procedures are to be completed within 28 days prior to C1D1 except for the following:

- Laboratory tests are to be performed within 3 days prior to C1D1. Except:
  - Hepatitis and HIV testing (if mandated by the local health authority) may be done up to 28 days prior to C1D1.

- Thyroid function tests may be done up to 10 days prior to C1D1.

Repeated laboratory evaluation to establish eligibility is not allowed unless discussed and agreed upon with the Sponsor.

- Full physical examination is to be performed within 7 days prior to C1D1.
- Evaluation of ECOG (or LPS, as appropriate) is to be performed within 3 days prior to C1D1.
- For women of reproductive potential, a urine or serum pregnancy test will be performed within 72 hours prior to C1D1. If urine pregnancy results cannot be confirmed as negative, a serum pregnancy test will be required (performed by the local study site laboratory).

### **Rescreening**

Participants may be rescreened after initially failing to meet the inclusion/exclusion criteria. Results from assessments during the initial Screening period are acceptable in lieu of a repeat screening test if performed within the specified time frame and the corresponding inclusion/exclusion criteria is met. Participants who are rescreened will retain their original screening number.

### **8.12.2 Treatment Period**

Visit requirements are outlined in Section 1.3 (SoA). Specific procedure-related details are provided in Section 8.1 through Section 8.11. Unless otherwise specified, the window for each visit is  $\pm 3$  days. Unless otherwise specified, assessments/procedures are to be performed prior to administration of study intervention.

### **8.12.3 Discontinued Participants Continuing to be Monitored in the Study**

#### **8.12.3.1 Safety Follow-up Visit**

The mandatory Safety Follow-up Visit should be conducted approximately 30 days after the last dose of study intervention or before the initiation of a new anticancer treatment, whichever comes first. If the EOT visit occurs  $\geq 30$  days after the last dose of study intervention, a Safety Follow-up Visit is not required. In this situation, all procedures required at the 30-day Safety Visit and EOT are performed once and entered into the EOT visit only.

#### **8.12.3.2 Follow-up Visits**

Participants who discontinue study intervention for a reason other than disease progression will move into the Follow-up Phase and should be assessed Q12W until Week 54 after C1D1 ( $\pm 7$  days), Q24W thereafter or sooner if clinically indicated or more frequently if required by local standard of care, until disease progression per RECIST 1.1, to monitor disease status. Every effort should be made to collect information regarding disease status until the start of

new anticancer therapy, disease progression, death, end of study. Information regarding poststudy anticancer treatment will be collected if new treatment is initiated. Participants who attain an investigator-determined CR and stop study intervention with pembrolizumab will have a Safety Follow-up Visit and move to follow-up visits per Section 1.3 (SoA).

### 8.12.3.3 Survival Follow-up

Participants who experience confirmed disease progression and are not treated beyond confirmed disease progression or start a new anticancer therapy, will move into the Survival Follow-up Phase and should be contacted by telephone approximately every 12 weeks to assess for survival status until death, withdrawal of consent, or the end of the study, whichever occurs first.

### 8.12.4 Survival Status

To ensure current and complete survival data is available at the time of database locks, updated survival status may be requested during the course of the study by the Sponsor. For example, updated survival status may be requested prior to but not limited to an external Data Monitoring Committee (eDMC) review, interim and/or final analysis. Upon Sponsor notification, all participants who do not/will not have a scheduled study visit or study contact during the Sponsor defined time period will be contacted for their survival status (excluding participants that have a previously recorded death event in the collection tool).

## 9 STATISTICAL ANALYSIS PLAN

This section outlines the statistical analysis strategy and procedures for the study. If, after the study has begun, changes are made to primary and/or key secondary objectives, or the statistical methods related to those objectives, then the protocol will be amended (consistent with ICH Guideline E-9). Changes to exploratory or other non-confirmatory analyses made after the protocol has been finalized but prior to the conduct of any analysis, will be documented in a supplemental Statistical Analysis Plan (sSAP) and referenced in the Clinical Study Report (CSR) for the study. Post hoc exploratory analyses will be clearly identified in the CSR.

### 9.1 Statistical Analysis Plan Summary

Key elements of the statistical analysis plan are summarized below. The comprehensive plan is provided in Sections 9.2 through 9.12.

Study Design Overview	A Phase 3 Open-label, Single Arm Study to Evaluate the Safety and Efficacy of Pembrolizumab (MK-3475) as First-line Therapy in Participants With Advanced Merkel Cell Carcinoma (KEYNOTE-913)
Treatment Assignment	Approximately 50 participants will be enrolled to treatment with pembrolizumab. This is a single-arm open-label study
Analysis Populations	Efficacy and Safety: All Participants as Treated (APaT)
Primary Endpoint	Objective Response (OR) per RECIST 1.1 by BICR

Secondary Endpoints	3. Duration of Response (DOR) per RECIST 1.1 assessed by BICR 4. Progression-free Survival (PFS) per RECIST 1.1 assessed by BICR 5. Overall Survival (OS)
Statistical Methods for Key Efficacy Analyses	Estimation of Objective Response Rate (ORR) and 95% exact binomial confidence interval (CI) for the true ORR; Estimation of PFS, OS, and DOR using the Kaplan-Meier method
Statistical Methods for Key Safety Analyses	Counts and percentages of participants with AEs
Interim Analyses	There are no planned interim analyses for this study
Multiplicity	No multiplicity adjustment is planned
Sample Size and Power	The planned sample size is approximately 50 participants. If the ORR is 56%, this sample size will produce a 95% CI for the true ORR of approximately $\pm 15\%$

## 9.2 Responsibility for Analyses/In-house Blinding

The statistical analysis of the data obtained from this study will be the responsibility of the Clinical Biostatistics department of the Sponsor. This study is being conducted as a nonrandomized, open-label study, ie, participants, investigators, and Sponsor personnel will be aware of participant treatment assignments after each participant is enrolled and treatment is assigned.

## 9.3 Hypotheses/Estimation

Objectives of the study are stated in Section 3. There are no hypotheses in this study.

## 9.4 Analysis Endpoints

Efficacy and safety endpoints that will be evaluated are listed below.

### 9.4.1 Efficacy Endpoints

#### 9.4.1.1 Primary

##### Objective Response Rate (ORR) per RECIST 1.1 assessed by BICR

The ORR is defined as the percentage of participants who achieve a confirmed complete response (CR) or partial response (PR) per RECIST 1.1 as assessed by BICR. Details of the ORR analysis can be found in Section 9.6.1.1.

#### **9.4.1.2 Secondary**

##### Duration of Response (DOR) per RECIST 1.1 assessed by BICR

For participants who demonstrate confirmed CR or PR, DOR is defined as the time from first documented evidence of CR or PR until disease progression or death due to any cause, whichever occurs first. Response duration will be calculated for RECIST 1.1 based on BICR by the imaging vendor. See Section 9.6.1.2 for the definition of censoring rules for DOR.

##### Progression-free Survival (PFS) per RECIST 1.1 assessed by BICR

PFS is defined as the time from the first day of study treatment to the first documented disease progression per RECIST 1.1 by BICR or death due to any cause, whichever occurs first. See Section 9.6.1.3 for the definition of censoring rules for PFS.

##### Overall Survival (OS)

OS is defined as the time from first day of study treatment to death due to any cause. Participants without documented death at the time of the final analysis will be censored at the last known alive date. To characterize the effects on survival, the final analysis of OS will be conducted approximately 13 years after the first participant signs informed consent/assent, when it is estimated that ~70% of participants will have died.

#### **9.4.2 Safety Endpoints**

Safety measurements are described in Section 4.2.1.2.

### **9.5 Analysis Populations**

#### **9.5.1 Efficacy Analysis Population**

The APaT population will serve as the population for the analysis of efficacy data in this study. The APaT population consists of all allocated participants who receive at least 1 dose of study treatment.

#### **9.5.2 Safety Analysis Population**

Safety analyses will be conducted in the APaT population as defined for efficacy.

At least 1 laboratory or vital sign measurement obtained subsequent to at least 1 dose of study treatment is required for inclusion in the analysis of the respective safety parameter. To assess change from baseline, a baseline measurement is also required.

### **9.6 Statistical Methods**

This section describes the statistical methods that address the primary and secondary objectives. Methods related to exploratory objectives will be described in the sSAP.

## 9.6.1 Statistical Methods for Efficacy Analyses

### 9.6.1.1 Objective Response Rate (ORR)

ORR will be calculated as the ratio of the number of participants reported to have achieved a confirmed CR or PR verified by BICR, divided by the number of participants included in the APaT population. Participants in the APaT analysis population without ORR assessments will be counted as non-responders. A 95% exact binomial CI based on the Clopper and Pearson method will be calculated for the true ORR.

### 9.6.1.2 Duration of Response (DOR)

The non-parametric Kaplan-Meier method will be used to estimate the DOR survival curve. Only the subset of participants with confirmed CR or PR response verified by BICR will be included in the analysis. 95% CIs for the median response duration and point estimates at various follow-up times will be calculated. The censoring rules for the analysis of DOR are summarized in [Table 8](#).

Table 8 Censoring Rules for Analysis of DOR

Situation	Date of Progression or Censoring	Outcome
No progression nor death, no new anticancer therapy initiated	Last adequate disease assessment	Censor (non-event)
No progression nor death, new anticancer therapy initiated	Last adequate disease assessment before new anticancer therapy initiated	Censor (non-event)
Death or progression immediately after $\geq 2$ consecutive missed disease assessments or after new anticancer therapy, if any	Earlier date of last adequate disease assessment prior to $\geq 2$ missed adequate disease assessments and new anticancer therapy, if any	Censor (non-event)
Death or progression after $\leq 1$ missed disease assessments and before new anticancer therapy, if any	Progressive disease or death	End of response (Event)
DOR=duration of response Note: A missed disease assessment includes any assessment that is not obtained or is considered inadequate for evaluation of response.		

### 9.6.1.3 Progression-free Survival

The non-parametric Kaplan-Meier method will be used to estimate the PFS survival curve. 95% CIs for the median PFS and PFS point estimates at various follow-up times from the first day of study treatment will be calculated.

Since disease progression is assessed periodically, PD can occur any time in the time interval between the last assessment where PD was not documented and the assessment when PD is documented. The true date of disease progression will be approximated by the earlier of the date of the first assessment at which PD is objectively documented per RECIST 1.1 by BICR and the date of death. Death is always considered a PD event. Participants who do not

experience a PFS event will be censored at the last disease assessment. The censoring rules for the analysis of PFS are summarized in [Table 9](#). If a participant meets multiple criteria for censoring, the censoring criterion that occurs earliest will be applied.

Table 9 Censoring Rules for Analysis of PFS

Situation	Date of Progression or Censoring
PD or death documented after $\leq 1$ missed disease assessment, and before new anticancer therapy, if any	Progressed at date of documented PD or death
PD or death documented immediately after $\geq 2$ consecutive missed disease assessments or after new anticancer therapy, if any	Censored at last disease assessment prior to the earlier date of $\geq 2$ consecutive missed disease assessment and new anticancer therapy, if any
No PD and no death; and new anticancer treatment is not initiated	Censored at last disease assessment
No PD and no death; new anticancer treatment is initiated	Censored at last disease assessment before new anticancer treatment
PD=progressive disease; PFS=progression-free survival	

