**1.2 Schema**

The study design is depicted in [Figure 1](#).

Figure 1 KEYNOTE-913 Study Design

BICR=blinded independent central review; C1D1=Cycle 1 Day 1; DOR=duration of response; ORR=objective response rate; OS=overall survival; PFS=progression-free survival; Q3W=every 3 weeks; Q12W=every 12 weeks; Q24W=every 24 weeks; RECIST=Response Evaluation Criteria In Solid Tumors

- a Prior adjuvant therapy may be allowed as detailed in Section 5.1, inclusion criterion #2.
- b Imaging to be performed Q12W or sooner if clinically indicated after C1D1 ( $\pm 7$  days) until Week 54 of study intervention, Q24W thereafter or sooner if clinically indicated, or more frequently if required by local standard of care, until disease progression per RECIST 1.1.
- c If End of Treatment visit occurs >30 days after last dose of study intervention, a Safety Follow-up Visit is not required.
- d For participants discontinuing for reasons other than disease progression, tumor imaging should continue to be performed as if on study intervention (ie, Q12W until Week 54 after C1D1 ( $\pm 7$  days), Q24W thereafter or sooner if clinically indicated, or more frequently if required by local standard of care, until disease progression per RECIST 1.1).
- e Participants in Survival Follow-up will be contacted approximately Q12W or sooner to assess for survival status or death, withdrawal of consent, or the end of study, whichever occurs first.

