Poststudy Anticancer Therapy						X	X	X	All anticancer therapy will be recorded until time of death or termination of Survival Follow-up. If a clinic visit is not feasible, follow-up information may be obtained via telephone or e-mail.

Study Period	Screening Phase	Intervention Phase (Q3W)			End of Treatment	Post-treatment Follow-up			Notes
		1	2	3 and onwards		Safety Follow-up a	Follow-up b	Survival Follow-up	
Treatment Cycle					Discontinuation				Procedures should occur predose on Day 1 of each cycle unless otherwise noted.  Post-treatment Period: Refer to Section 8.12.3.
Scheduled Timing	-28 to -1				At time of d/c	30 days post last dose		~Q12W (telephone)	
Window (days):		+ 3	± 3	± 3		+ 7	± 7	± 7	
Survival Status		<----->						X	After investigator-determined PD or start of new anticancer treatment. In addition, upon Sponsor request, participants may be contacted for survival status at any time during the course of the study (unless this information is not allowed to be provided due to confidentiality).
Efficacy Procedures									
Tumor Imaging (CT/MRI; Chest, Abdomen, and Pelvis)	X	<-----> c			X d			X	Prior scans performed within the screening period but before signing informed consent may be used if consistent with protocol requirements per SIM. All imaging visits have a scheduling window of ±7 days. Imaging to be performed Q12W or sooner if clinically indicated from the date of C1D1 until Week 54 of study treatment, Q24W or sooner if clinically indicated thereafter, or more frequently if required by local standard of care until disease progression per RECIST 1.1.

Study Period	Screening Phase	Intervention Phase (Q3W)			End of Treatment	Post-treatment Follow-up			Notes
		1	2	3 and onwards		Safety Follow-up a	Follow-up b	Survival Follow-up	
Treatment Cycle					Discontinuation				Procedures should occur predose on Day 1 of each cycle unless otherwise noted.  Post-treatment Period: Refer to Section 8.12.3.
Scheduled Timing	-28 to -1				At time of d/c	30 days post last dose		~Q12W (telephone)	
Window (days):		+ 3	± 3	± 3		+ 7	± 7	± 7	
Safety Procedures									
Height	X	X	X	X	X				Pediatric height to be measured at every visit. Adult height measured at Screening only.
Weight	X	X	X	X	X				To be measured at every visit.
Full Physical Examination	X								Within 7 days prior to C1D1.

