#### 9.6.1.4 Overall Survival

The non-parametric Kaplan-Meier method will be used to estimate the OS survival curve. 95% CIs for the median OS and OS point estimates at various follow-up times from the first day of study intervention will be calculated. Participants without documented death at the time of analysis will be censored at the date the participant was last known to be alive.

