### 9.7 Interim Analyses

No interim analyses are planned in this study.

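### Do the undated ORR, DOR and PFS analyses, the unnamed landmark times and the off-grid Week 54 leave the efficacy estimates undetermined?

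*Combined protocol and SAP*

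**What the plan says.** **Analysis time.** The endpoint definition for OS in Section 9.4.1.2 states that "the final analysis of OS will be conducted approximately 13 years after the first participant signs informed consent/assent". Section 9.7 adds: "No interim analyses are planned in this study". No data cut-off or minimum follow-up is given for ORR, DOR or PFS. Section 8.12.4 nevertheless says that "updated survival status may be requested prior to but not limited to an external Data Monitoring Committee (eDMC) review, interim and/or final analysis".

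**Landmarks.** For PFS: "95% CIs for the median PFS and PFS point estimates at various follow-up times from the first day of study treatment will be calculated". For DOR: "95% CIs for the median response duration and point estimates at various follow-up times will be calculated". For OS: "95% CIs for the median OS and OS point estimates at various follow-up times from the first day of study intervention will be calculated". No months are named.

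**Scan weeks.** The Schedule of Activities has "Imaging to be performed Q12W or sooner if clinically indicated from the date of C1D1 until Week 54 of study treatment", and the Schema continues "until Week 54 of study intervention, Q24W thereafter or sooner if clinically indicated". Sections 4.1 and 8.2.1.2 agree and attach a ±7-day window to Week 54. None of them says whether a scan is due at Week 54, or from which week the 24-week interval runs. Tables 8 and 9 censor a progression or death that follows two or more consecutive missed assessments, and they list no assessment weeks.

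**The concern.** Section 4.2 makes robust ORR and durable response the basis on which the study would support the postmarketing requirement, so one expects to see when these are analysed. If a report came before year 13, no written rule would fix its cut-off. Unnamed landmarks allow a favourable time point to be picked. The scan calendar looks the most serious of the three. One participant with one set of scans can be a PFS event under one reading and censored months earlier under another. KEYNOTE-017's median PFS of 16.8 months also falls in the stretch where the calendar is unclear.

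**Working it through.** **1. ORR and the cut-off.** The plan's own figure first. The Clopper-Pearson interval for 28/50 runs from the 2.5% quantile of Beta(28, 23) to the 97.5% quantile of Beta(29, 22). That is 41.25% to 70.01%, matching Table 11. Section 2.2.1.3 reports that 26 of KEYNOTE-017's 28 responses had occurred by the first on-study scan. Counting only those gives 26/50 = 52% (37.4% to 66.3%), against 56% (41.3% to 70.0%) for all 28. Even the earliest conceivable cut moves ORR by only 4 points, and a year-13 analysis would include every response.

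**2. Scan calendars.** 54/12 = 4.5, so the 12-week visits are Weeks 12, 24, 36 and 48. Four continuations are possible. The last two columns give the week after which a progression or death counts as following two missed scans (second missed visit plus the 7-day window).

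| Reading | Next scans | Last scan Week 36 | Last scan Week 48 |
|---|---|---|---|
| A: 24 weeks from Week 48 | 72, 96 | 73 | 97 |
| B: scan at 54, then 24 weeks | 54, 78 | 55 | 79 |
| C: no scan at 54, 24 weeks from 54 | 78, 102 | 79 | 103 |
| D: next 12-week point, then 24 weeks | 60, 84 | 61 | 85 |

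Example: last adequate scan at Week 36, Week 48 missed, PD seen at Week 72. Under A and C one visit is missed, so this is an event at Week 72. Under B and D two are missed, so the participant is censored at Week 36. The ambiguity is therefore real.

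**3. What the reading can and cannot move.** Section 9.6.1.3 dates progression at the assessment that documents it. Once the scans exist, no reading of the schedule changes that date. KEYNOTE-017's median of 16.8 months is Week 73.0 (16.8 x 4.348). It would be recorded at different weeks if sites scanned on different calendars, but that compares different scan conduct, not different analyses of one dataset. For fixed data, only the missed-scan count is affected.

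**4. How many participants.** From the table, the readings disagree only for events between about Week 55 and Week 103, that is, months 12.7 to 23.7 (weeks/4.348). This covers participants whose last adequate scan was Week 36 or 48, where the calendars diverge. KEYNOTE-017's PFS was 52% at 12 and 16 months and 48% at 18 and 24 months. With n = 50 and no other censoring, the drop is 50 x (0.52 - 0.48) = 2 participants. With 5-15% of scans missed (assumed), the expected number affected is 2 x 0.05 = 0.1 to 2 x 0.15 = 0.3.

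**5. Effect on 18-month PFS.**
- Both counted as events: 24/50 = 48.0%.
- One censored at Week 36, one event, no events between: 0.52 x 24/25 = 49.9%, a shift of 1.9 points.
- Expected shift: 0.1 x 1.9 = 0.2 to 0.3 x 1.9 = 0.6 points.
- Both censored (the extreme case): 52%, a shift of 4 points.
- Sampling half-width at 48%, n = 50, binomial approximation: 1.96 x sqrt(0.48 x 0.52/50) = 13.8 points.

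**6. Effect on 12-month PFS.** Censoring at Week 36 can also touch this estimate. Suppose 28 are at risk and two events occur at Week 48. Then 0.56 x 26/28 = 52.0% becomes 0.56 x 25/27 = 51.9%. The interval for 26/50 is 37.4% to 66.3%. A 3.1-month median on chemotherapy (Section 2.2.1.2), taken as exponential, implies 0.5^(12/3.1) = 6.8%. The contrast does not depend on the reading.

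**The case for a change.** The strongest reply is that these details belong in this document and cost only wording. Section 9.6 says it holds the primary and secondary methods and leaves only exploratory ones to the supplemental SAP, so nothing else is promised to supply them. Tables 8 and 9 cannot be programmed without a list of visits. Deaths are affected as well: with the last scan at Week 48 and none after, a death at Week 80 is censored under reading B and is an event under A, C and D. The cut-off also determines what can be reported. If the true 24-month PFS is 48% and all participants have 24 months of follow-up, the chance that at least 26 of 50 are event-free, leaving the median unreached, is 33.5%.

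All of that is factually right, but it does not show a defective analysis. An unreached median is an ordinary Kaplan-Meier result, reported as such with its curve, and no decision rule depends on it. The literal reading, a single final analysis at about 13 years, agrees with the study duration in the synopsis and gives more follow-up, not less. The interim wording in Section 8.12.4 is generic: it also mentions an external monitoring committee, although Section 10.1.4 plans no committees. Landmarks are read from a curve that is estimated in full, so a selectively chosen one would be visible. The programmer's missing list is a real omission, but the recorded scan dates will show which calendar sites followed, and any sensible list gives nearly the same result.

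**Conclusion.** No change to the plan is needed. The omissions are real: an unstated analysis time for ORR, DOR and PFS, unnamed landmarks, and a Week 54 that lies off the 12-week grid. They are details that analysts can settle without harm. The study has no hypothesis (Section 9.3), so no error rate is at stake, and writing the details down would not introduce a better method. The only effect on a fixed dataset is through the missed-assessment count: 0.1 to 0.3 participants expected, and about 0.2 to 0.6 points on 18-month PFS against a half-width of about 14 points. The ORR is unaffected by the scan weeks in doubt, and the contrast with chemotherapy is unchanged.

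This rests on KEYNOTE-017's PFS pattern recurring in 50 participants with no other censoring, on 5-15% of scans being missed (the documents give no rate), and on the affected participants having their last adequate scan at Week 36 or 48. In the extreme case, with both participants behind the late drop censored, 18-month PFS moves by 4 points and the median is no longer reached at 18 months. Even that is well inside sampling error.

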#### 9.6.1.5 Analysis Strategy for Key Efficacy Endpoints

[Table 10](#) summarizes the analysis approach for key efficacy endpoints.

Table 10 Analysis Strategy for Key Efficacy Endpoints

Endpoint	Statistical Method a	Analysis Population	Missing Data Approach
Primary Endpoints			
ORR per RECIST 1.1 by BICR	Estimation : Exact method based on binomial distribution (Clopper-Pearson method)	APaT	Participants without assessments are considered non-responders and conservatively included in the denominator
Key Secondary Endpoint			
DOR per RECIST 1.1 by BICR	Estimation : Summary statistics using Kaplan-Meier method	Participants in APaT population with an objective response	Non-responders are excluded from analysis; Responders are censored according to rules in Table 8

Endpoint	Statistical Method a	Analysis Population	Missing Data Approach
PFS per RECIST 1.1 by BICR	Estimation : Summary statistics using Kaplan-Meier method	APaT	Censoring according to Table 9
OS	Estimation : Summary statistics using Kaplan-Meier method	APaT	Censored at the last known alive date
APaT=All Patients as Treated; BICR=blinded independent central review; DOR=duration of response; ORR=objective response rate; OS=overall survival; PFS=progression-free survival; RECIST=Response Evaluation Criteria in Solid Tumors a Statistical methods are described in further detail in the text.			

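### Section 9.6.1.3 says death is always a PD event, but Table 9 censors some deaths; the sentence misstates the PFS analysis, and this protocol/SAP has no analysis under the endpoint definition

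*Combined protocol and SAP*

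**What the plan says.** Section 9.4.1.2 defines PFS as time from first treatment to BICR-documented PD or death from any cause, whichever is first, and adds "See Section 9.6.1.3 for the definition of censoring rules for PFS". Section 9.6.1.3 then gives the rules in two forms.

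- **Text.** The progression date is the earlier of first BICR-documented PD and death. The next sentence is "Death is always considered a PD event". Only participants without a PFS event are described as censored.
- **Table 9, row 2.** The situation begins "PD or death documented immediately after" and covers two triggers: at least two missed assessments in a row, or new anticancer therapy. The outcome begins "Censored at last disease assessment prior to the earlier date of", that is, the earlier of those two triggers.

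Between them stands a tie-break: "If a participant meets multiple criteria for censoring, the censoring criterion that occurs earliest will be applied". Table 10 (Section 9.6.1.5) gives the missing-data approach for PFS as "Censoring according to" Table 9 and lists no other approach. Section 9.6 says of itself: "This section describes the statistical methods that address the primary and secondary objectives".

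**The concern.** A death that meets row 2 is an event under the text and censored under the table, so both cannot describe the same analysis. A reader of the text, or of the any-cause definition, would take the reported PFS curve, median and landmark rates to include every death. Under Table 9 some known deaths are left out, and nothing in this protocol/SAP would show how many or what difference they make.

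The new-therapy trigger is a foreseeable case. Under Section 8.2.1.2, protocol scans end at investigator-identified PD or at the start of new treatment, whereas the endpoint needs BICR PD. Survival follow-up goes on after new therapy (Section 8.12.3.3). A participant who changes treatment before BICR PD and later dies therefore has a known death that row 2 sets aside.

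**Working it through.** **1. The two rules, case by case**

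| Participant | Text of 9.6.1.3 and definition in 9.4.1.2 | Table 9 |
|---|---|---|
| Dies without BICR PD, at most one missed assessment, no new therapy | Event at death | Event at death (row 1) |
| Starts new therapy without BICR PD, later dies | Event at death | Censored at last assessment before new therapy (row 2) |
| Misses two scans in a row, then dies without PD | Event at death | Censored at last assessment before the gap (row 2) |
| Misses two scans in a row, then has BICR PD | Event at that PD | Censored at last assessment before the gap (row 2) |

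The rules agree only in the first case. The tie-break sentence ranks one censoring criterion against another; it does not say when a death stops being an event.

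**2. Which rule governs.** The definition sends the reader to Section 9.6.1.3 for censoring, that section points to Table 9, and Table 10 names Table 9 alone. Table 9 is the operative rule.

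**3. Is there a second analysis?** Sections 9.1 to 9.12 contain none for BICR PFS, and no count of censored PDs or deaths. The only other PFS analysis is exploratory, by investigator iRECIST (Section 3).

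**4. Size, by illustration.** The plan gives no PFS event count or precision to reproduce; Section 9.9 concerns ORR only. A curve for n = 50 was therefore rebuilt from the earlier pembrolizumab study in Section 2.2.1.3.

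Inputs from the document:
- PFS 52% at 12 months: 24 events by then.
- Median 16.8 months: 25th event.
- PFS 48% at 18 and 24 months: 26 events by 18 months.
- PD as best response in 32%.

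Assumptions:
- 16 events by week 12 (0.32 × 50), leaving 34 at risk.
- 18 events by week 24 (the other 8 first-year events spread evenly), leaving 32 at risk.
- No other censoring.
- k = 1, 2 or 3 affected deaths, each censored at a last scan at week 12 or week 24.

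With all deaths counted: 24-month PFS = 24/50 = 48.0%; 12-month PFS = 26/50 = 52.0%.

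*Deaths between the last scan and 24 months.* 24-month PFS under Table 9:
- Last scan week 12: (34/50) × 24/(34 − k) = 49.5%, 51.0%, 52.6%.
- Last scan week 24: (32/50) × 24/(32 − k) = 49.5%, 51.2%, 53.0%.

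The shift is +1.5 to +5.0 points. For k = 2 or 3 the curve is still above 50% at 24 months, so the median goes from 16.8 months to not reached by then.

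*Deaths after 24 months.* 12-month PFS under Table 9:
- Last scan week 12: (34/50) × (26 − k)/(34 − k) = 51.5%, 51.0%, 50.5%.
- Last scan week 24: (32/50) × (26 − k)/(32 − k) = 51.6%, 51.2%, 50.8%.

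The shift is −0.4 to −1.5 points. The next event, at 16.8 months, takes the curve below 50% in each case (for k = 1, week 12: 0.68 × 24/33 = 49.5%), so the median stays at 16.8 months.

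*Cross-check.* In a simulation with the first 24 events spread evenly from 1.5 to 11.8 months, affected events were drawn at random and each was censored at the preceding 12-weekly scan. Mean 24-month PFS was 49.3%, 50.6% and 52.0% for k = 1, 2 and 3. The median was not reached in 99% of draws for k = 2.

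**The case against.** The best defence is that the sentence says PD event, not PFS event. It follows the sentence on how the progression date is approximated, and both event rows of Table 9 speak of PD and death together. On that reading death is simply classed with PD, and both then go through Table 9. This is plausible, and it supports Table 9 as the rule. It does not rescue the word *always*, nor does it square the date rule and the any-cause definition with row 2.

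Correcting the sentence would by itself remove the contradiction in the text. That is true, but the endpoint definition would still go unestimated and the events set aside would still go uncounted.

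The supplemental SAP could hold such an analysis. Section 9.6 assigns exploratory methods to it, and Section 9 also allows changes to other non-confirmatory analyses there. It was not among the documents, so the absence is claimed for this protocol/SAP only.

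Four stronger readings are tempting and not supported:
- *That Table 9 is the wrong rule.* Neither rule is neutral. Counting every death credits unscanned time as progression-free: at least about 24 weeks after two missed 12-weekly scans, and 48 after two 24-weekly scans.
- *That Table 9 always flatters PFS.* The illustration moves in either direction, depending on when the deaths occur.
- *That DOR has the same contradiction.* Table 8 censors similarly, but Section 9.6.1.2 has no sentence saying that death always counts.
- *That the shifts are harmless because they lie within a sampling confidence interval.* Both rules use the same participants, so sampling error is not the yardstick.

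**Conclusion.** The point stands as an error of statement and a reporting gap. Table 9 governs, the unqualified sentence misdescribes it, and this protocol/SAP contains neither a BICR PFS analysis under its own endpoint definition nor a count of what row 2 removes.

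No expected effect can be given, because the number of affected PDs and deaths cannot be derived from the documents. The figures above rest on 1 to 3 assumed deaths and on a curve from another study whose censoring rules are not stated, so they are not a forecast or a comparison with that study. The possible loss of the median reflects a curve that is flat near 50%.

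A reader might infer that the trial's main conclusions are at risk. The documents do not support that. There are no hypotheses (Section 9.3), PFS is a descriptive secondary endpoint, Section 4.2 rests the postmarketing case on ORR and durable responses, and ORR and OS do not depend on this rule. The correction is still worth making, since the median and landmark PFS rates will be reported and readers need to know which deaths they include.

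**What to change.** 1. In Section 9.6.1.3, replace the sentence with: *Death is treated as a PD event and is counted or censored according to Table 9.*
2. Keep Table 9 as the main rule. Add one PFS sensitivity analysis that follows the endpoint definition: the first BICR-documented PD or death from any cause, whichever is first, is an event on its date, regardless of missed assessments or new anticancer therapy. It should release late PDs as well as deaths. Otherwise a participant with BICR PD after a two-scan gap who then dies could stay censored while an unscanned participant who dies counts as an event.
3. Report the number of PDs and of deaths censored by row 2, split by reason (missed assessments; new anticancer therapy).

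Optional tidying: carry Table 8's requirement that the last assessment be adequate, and its note on what counts as missed, into Table 9.

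Cost: one wording change, one extra Kaplan-Meier run and one count. No new data are needed, since anticancer therapy is recorded until death or the end of survival follow-up (Section 6.5) and deaths are collected for OS. Late PFS may look slightly less favourable in the sensitivity analysis.
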